3.3 Study sites

This study will be conducted in Manaus and Porto Velho, reference centers for malaria diagnosis and treatment which already perform gold standard diagnosis of G6PD because of concomitant clinical trials in which this information is key (e.g., tafenoquine trials).

These centers are also responsible for technical supervision and training of other teams working in the primary care in the municipalities. Therefore, these sites have access to lower levels of health care service delivery.

4.0 Research participants

4.1 Characteristics of research participants

Participants:

Participants for this study will include both febrile patients seeking care at the Manaus and Porto Velho clinics and participants recruited via an enriched sample with known G6PD status established through previous epidemiological studies. Approximately half of the total participants will be recruited from each patient population. Participants with known G6PD recruited from the previous epidemiological studies have agreed to have their G6PD status retained and to be contacted again for participation in future studies as part of the informed consent process.

Health workers:

The health workers recruited for participation in this study will be representative of intended end users of point of care G6PD tests, as per requirements of the WHO PQ. This will include both health care providers such as community health workers, and laboratory technicians who perform malaria rapid diagnostic tests and other malaria testing near the point of care.

4.2 Inclusion and exclusion criteria

4.2.1 Participant with unknown G6PD status

Inclusion criteria:

- Seeking care at the Manaus or Porto Velho clinics
- 2 years age or older
- Willing to provide informed consent

Exclusion criteria

- Younger than 2 years of age
- Participants who received a blood transfusion in the last 3 months, self-report
- Unwilling to provide informed consent

4.2.2 Participant with known G6PD status

Inclusion criteria:

- Included in previous G6PD surveys and provided consent to be contacted again
- 2 years of age or older
- Willing to provide informed consent or assent

Exclusion criteria:

- Younger than 2 years of age
- Participants who received a blood transfusion in the last 3 months, self report
- Unwilling to provide informed consent or assent or unavailable during study visit

4.2.3 Health worker:

Inclusion criteria:

[figure not shown]
- Provides malaria case management at study facility or study site
- Considered an intended user of quantitative POC G6PD tests
- Trained and proficient in the use of the POC G6PD test
- Willing to provide informed consent

Exclusion criteria:

- Does not provide malaria case management at study facility or study site
- Not considered an intended user of quantitative POC G6PD tests
- Not trained or is not considered proficient in the use of the POC G6PD test
- Unwilling to provide informed consent

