Evaluation of a diagnostic to identify G6PD deficiency in Brazil

Version 5
May 2019

Investigators:

Location of Research:

Manaus and Porto Velho, Brazil

Proposed Project Dates:

May-December 2019

Study Title	Validation of diagnostics to identify G6PD deficiency in Brazil
Précis	Cross-sectional diagnostic accuracy study with 2,000 patient participants and 15 health worker participants. The participant population will be recruited at clinics and through a household survey using an enriched sample of a population with known G6PD status, established through previous epidemiological studies. The health worker participants will include trained intended users of the G6PD tests. Health workers will take capillary blood samples and conduct two point of care tests: 1) hemoglobin test, and 2) investigational point-of-care (POC) G6PD test. A thick blood slide will also be prepared for malaria microscopy. Venous blood will be collected and transferred to a laboratory where reference assays will be performed on venous samples using the Pointe Scientific G6PD Analyzer and hemoglobin tests. Trained health workers will also be surveyed to assess product usability through a questionnaire to assess label and packing comprehension as well as results interpretation.
Objectives	
Primary Objective: To assess the accuracy and reliability of G6PD tests in detecting G6PD activity and classifying results when used by trained health care workers in Brazil.
 
Component Objectives:
 
 • To determine the performance of G6PD tests in detecting G6PD activity and hemoglobin (Hb) compared to a reference assay • To assess the comprehension of the G6PD test packaging and labelling among intended users • To assess the usability of G6PD test result outputs among intended users

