The estimated prevalence of G6PD activity at less than 30% of normal enzyme activity is 5% in Brazil [16]. In Brazil, testing a minimum of 2,000 individuals is expected to generate approximately 100 deficient and 200 intermediate individuals. These data will be combined with data from other clinical evaluation sites in Ethiopia and India. The estimated prevalence of G6PD activity at less than 30% of normal enzyme activity is 2.5% in Ethiopia and 5% in India [16]. In Ethiopia, testing a minimum of 1,500 individuals is expected to generate approximately 38 deficient and 75 intermediate individuals and in India testing a minimum of 1,000 individuals is expected to generate approximately 50 deficient and 100 intermediate individuals. By combining the data from multiple clinical sites, these studies will reach the target number of samples required by WHO PQ.

Per guidance from the WHO PQ and US FDA guidelines for usability testing, 15 purposively selected intended users of POC G6PD tests will be sampled for the usability assessment across both study sites [15] [17]. As in the diagnostic performance assessment, the data from this usability assessment will be combined with data from a similar sample of health workers in other evaluations (a minimum of 15 in each Brazil and India) in order to reach the target number of users required by WHO PQ.

Participant group	Recruitment sample size	Target enrollment sample size
Participants	2,200	2,000
Health workers trained in the use of the G6PD test	18	15

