5.2.3 Screening and consent-household visits

For participants with known G6PD status, the study team will use the recruitment script to recruit participants in their homes. Only members of the household who have a known G6PD status from past epidemiological studies will be eligible for participation. Other household members will not be asked to participate in the study. He or she will be screened for inclusion in the study. The study team will explain the study and invite the person to participate. If the person expresses interest in participating in the study, she or he will be directed to a private space for consenting. Written consent or assent will be obtained from all participants. See detailed consent procedures and explanation of ethical considerations in sections 6.0 and 10.0.

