5.5 Summary of study procedures

Table 6. Summary of study procedures

Participant group	List of study procedures	Estimated time	Data collection forms used
Health workers	
 • Training on the use of POC G6PD tests • Consent and enrolment • Usability assessment questionnaire 	
 • Up to 5 hours • 20 minutes • 20 minutes 	
 • Appendix A2
Children aged 2-18	
 • Assent, parental permission, and enrollment • Conduct POC tests and blood draw 	
 • 20 minutes • Up to 30 min 	
 • Appendix A1
Adults	
 • Consent and enrolment • Conduct POC tests and blood draw 	
 • 20 minutes • Up to 30 min 	
 • Appendix A1

Figure 3. Participant flow and follow-up procedures

*Vivax positive patients, recruited from the enriched sample of participants known to be G6PD deficient or intermediate, may receive a false negative G6PD normal result from the investigational POC test. In the event this occurs, this subpopulation will be considered G6PD intermediate/deficient and provided counseling and a counselling card as described in section 5.4.

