12.0 Study limitations

There are some limitations to this diagnostic evaluation. With regard to any diagnostic accuracy evaluation, there are opportunities for bias. This study will rely on the quantitative spectrophotometer assay as the reference test rather than genetic sequencing and an imperfect reference test may lead to classification bias. Given the rates of G6PD prevalence in Brazil and the data requirements in the WHO verification guidelines, some purposive sampling will be required and we expect a significant number of the samples tested in Brazil to be G6PD normal. Finally, given the wide range of potential end users of POC G6PD tests globally and across different segments of the health system, the results of the usability assessment may not be generalizable outside of the study sites.

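### The household stream is called enriched, but no visible rule selects people by prior G6PD status, and the case forecast is unenriched prevalence, below the plan's own target for deficient participants

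*Combined protocol and SAP*

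**What the plan says.** The synopsis says that participants come from clinics and "through a household survey using an enriched sample of a population with known G6PD status, established through previous epidemiological studies". Section 4.1 repeats the idea and fixes the split: "Approximately half of the total participants will be recruited from each patient population". Section 3.2 says the enriched sample also serves the WHO prequalification requirements, and section 12.0 says that "some purposive sampling will be required and we expect a significant number of the samples tested in Brazil to be G6PD normal".

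The text that sites would apply does not mention which status a person must have. Section 4.2.2 admits a person who was "Included in previous G6PD surveys and provided consent to be contacted again", with age and consent conditions. Section 5.2.3 adds: "Only members of the household who have a known G6PD status from past epidemiological studies will be eligible for participation". The footnote to Figure 3 speaks of patients "recruited from the enriched sample of participants known to be G6PD deficient or intermediate".

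On numbers, section 3.2 states that "The estimated prevalence of G6PD activity at less than 30% of normal enzyme activity is 5% in Brazil" and that "testing a minimum of 2,000 individuals is expected to generate approximately 100 deficient and 200 intermediate individuals". The synopsis gives the matching 1,700 normal and says that the mix rests on estimated prevalence. Section 3.2 also sets a minimum of 162 deficient and intermediate participants together, and then asks for at least 200 in each of those two groups. It plans to combine the Brazilian data with data from Ethiopia (38 deficient, 75 intermediate) and India (50 and 100).

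**The concern.** Deficient and intermediate participants determine how precisely sensitivity is estimated. Within Brazil, people of already known status are the plan's means of raising their number without raising total enrolment. That works only if status decides who is approached. The visible text gives no quota, ratio, priority order or sex rule, although Table 2 gives an intermediate class to women only. Two sites could both follow the protocol and return very different case mixes, with no planned number to monitor against.

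The forecast does not fill the gap, because it appears to ignore enrichment. If it is right, the plan misses its own per-group target for deficient participants. If enrichment will in fact happen, the forecast is wrong and the expected counts are unknown.

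**Working it through.** **Inputs.** Total 2,000, prevalence of deficiency 5%, forecast 100 deficient and 200 intermediate, target of at least 200 per group, combined minimum 162, and the figures for Ethiopia and India (all section 3.2); 1,700 normal (synopsis); about half the participants from each stream (section 4.1).

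**1. Reproduce the forecast (N × prevalence).**
- Brazil: 2,000 × 0.05 = 100 deficient, as stated. Intermediate: 200/2,000 = 10%, implied and not stated.
- Ethiopia: 1,500 × 0.025 = 37.5, stated as 38. India: 1,000 × 0.05 = 50, as stated.
- In all three countries the intermediate count is twice the deficient count before rounding (200, 75 and 100).

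The Brazilian forecast thus uses the same rule as the other two countries, with background prevalence applied to all 2,000 and nothing added for the household half.

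**2. What the forecast implies for the household half.** Even if all 1,000 clinic participants were normal, 1,700 − 1,000 = 700 household participants would still have to be normal. If instead the household half held only deficient or intermediate people, as the Figure 3 footnote can be read, and clinics ran at background (15% non-normal), there would be about 1,000 × 0.85 = 850 normals in total, not 1,700. The forecast and that reading of the footnote cannot both describe the sample.

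**3. Compare with the targets.**
- Deficient, Brazil alone: 100 against 200. With 2,000 people at 5%, the binomial probability of 200 or more is about 6 × 10⁻²⁰.
- Deficient, pooled: 100 + 38 + 50 = 188, still below 200.
- Intermediate: 200 expected in Brazil, so the target is met on average (binomial probability about 0.51); pooled, 200 + 75 + 100 = 375.
- Deficient plus intermediate: 100 + 200 = 300 in Brazil, above 162.

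The shortfall is in the deficient group only.

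**4. What the household half would have to supply.** Assume clinics run at 5%, giving 1,000 × 0.05 = 50 deficient.
- For 200 in Brazil: 200 − 50 = 150 of 1,000 (15%, three times background).
- For 200 pooled: 200 − 38 − 50 − 50 = 62 of 1,000 (6.2%).

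**5. Effect on precision at the 30% threshold (exact Clopper-Pearson 95% limits).** With n of n correct, the lower limit is 0.025^(1/n).

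| Deficient participants | Lower limit, perfect result |
|---|---|
| 100 (Brazil, forecast) | 96.4% |
| 200 (Brazil, enriched) | 98.2% |
| 188 (pooled, forecast) | 98.1% |
| 288 (pooled, Brazil enriched by 100) | 98.7% |

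At an observed 95% in Brazil, the interval is 88.7–98.4% with 95/100 and 91.0–97.6% with 190/200.

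**6. Cost in specificity.** Taking 95% specificity for illustration and counting only the normals, the interval is 93.9–96.0% with 1,700 and 93.8–96.0% with 1,600.

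**The case against.** The strongest reply is that eligibility is not selection. Section 4.2.2 says who may enter, not who is visited. Statuses are retained and contact is in person, so staff could favour known deficient and intermediate people without breaking any criterion. The synopsis and sections 3.2, 4.1 and 12.0 all say that enrichment is meant. This stands. A reader might infer that the household stream enriches nothing, has an enrichment factor of 1, or spends about 850 of its 1,000 visits on known normals. The documents do not support those statements: they treat a permissive criterion as a sampling rule and a forecast that omits enrichment as proof that none occurs. The status mix of the earlier surveys is not given.

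Other parts of the reply also stand:
- The household stream is not the only route to more cases, because section 3.2 pools with Ethiopia and India. On the pooled base the gain in the lower limit is smaller.
- Section 3.2 sizes sensitivity on deficient and intermediate participants together, and that minimum is met without enrichment.
- The primary success criterion in section 3.1.1 concerns specimens below 20% of normal, so limits computed for the group below 30% are not limits for that criterion.
- The Figure 3 footnote may describe only a subset of the household stream; section 5.4 can be read that way.
- The figures and the recruitment appendix are not visible, so a contact rule could be stated there.
- If the earlier surveys ran at 5%, finding 150 known deficient people would take 150/0.05 = 3,000 previously surveyed people, all contactable and willing.

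None of this supplies a selection rule in the visible text or reconciles the forecast with the target of 200 deficient participants.

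**Conclusion.** The concern holds in a limited form: enrichment is named but not put into operation. The criteria do not depend on prior status, no visible rule or quota selects by it, and the forecast equals background prevalence times 2,000. The household yield is therefore undetermined, not shown to be at background.

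Measured against the plan's own figures, expected deficient numbers are 100 in Brazil or 188 pooled, short of 200 on either reading of the target. The intermediate group and the combined minimum are not short on expectation.

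The gain in precision is illustrative. It assumes clinics at 5%, and that about 150 known deficient people can be contacted for the Brazilian target (about 62 for the pooled one). The documents give no basis for judging either number. The point deserves correction before recruitment because the remedy needs no extra participants and costs almost nothing in specificity.

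**What to change.** - In sections 4.2.2 and 5.2.3, state that the household contact list is selected by prior status: all contactable people previously classed as deficient (either sex) or intermediate (women), plus known normals up to the planned number.
- Issue the list in mixed order and withhold prior status from the staff who run the point-of-care test. Visiting the cases first would let the order of visits reveal status, and the blinding described in section 5.2.5 covers laboratory operators only.
- Keep enrolment at 2,000.
- In section 3.2 and the synopsis, give expected counts separately for the clinic and household streams, using the number of contactable people in each status group. Say whether the target of 200 per group applies to Brazil or to the pooled data, and restate it if it cannot be met.
- Make the Figure 3 footnote describe the same household sample as sections 4.2.2 and 5.2.3.

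The cost is a protocol amendment and a contact list drawn from statuses already retained with consent. The drawbacks are slightly wider specificity intervals and a case mix further from the natural one. The latter should be acknowledged in section 12.0.

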5.0 Study procedures

Figure 1. Study process

5.1 Usability assessment

5.1.1 Screening and recruitment

First, study staff will conduct an orientation for laboratory managers and health workers to explain the study, its objectives, and what participation will entail. At the orientation, the study staff will explain that participation is voluntary, that it will not affect their employment, and ask managers and supervisors to emphasize the voluntary nature of participation among their staff. Health workers who meet the above inclusion and exclusion criteria will be identified by study staff through discussions with laboratory managers and invited to participate in a training on G6PD testing. Health workers will be recruited purposively based on whether their role aligns with a use case for the POC G6PD tests and in order to obtain a representative sample of intended users of the POC G6PD test. Once identified, health workers will be study staff will explain the study and invited health workers to participate in a private setting, and if they express interest, they will be consented and enrolled into the study.

5.1.2 Training and data collection

Training content will be developed and delivered in collaboration with the relevant health administrators at the study site and the test developers. The study team will train health workers at the study site in the proper use of all POC tests being evaluated and the reference assay. Health workers will be certified as proficient in the assays as determined by the study team. Any health worker not certified as proficient will have the opportunity

to receive additional training. Records of the user proficiency assessment and certification will be kept as study documents and not shared with the laboratory managers or supervisors. Trained health workers will then be given a questionnaire to assess test label comprehension and results interpretation. At that time, the study staff will emphasize the participants that the questionnaire is being used to assess the effectiveness of the training content and test instructions, and not the skills or performance of the user.

5.2 Diagnostic performance assessment

5.2.1 Recruitment

Screening of participants with unknown G6PD status will occur at the clinics in Manaus and Porto Velho and collaborating health facilities in the clinical catchment area. At clinics, the study team will use the recruitment script to recruit participants in the public areas, such as the waiting areas, of the clinics. Recruitment will be conducted in such a way as to not interfere with the potential participant's care.

Recruitment of participants with known G6PD status will take place at through home visits conducted by the study staff. Participants who were previously involved in epidemiological studies will be contacted in person by the study team and screened against inclusion criteria. Participants with known G6PD recruited from the previous epidemiological studies have agreed to have their G6PD status retained and to be contacted again for participation in future studies as part of the informed consent process.

5.2.2 Screening and consent-clinics

Study staff will screen participants for eligibility. The study team will explain the study and invite the person to participate. If the person expresses interest in participating in the study, she or he will be directed to a private space for consenting. Written consent or assent will be obtained from all participants. See detailed consent procedures and explanation of ethical considerations in sections 6.0 and 10.0.

5.2.3 Screening and consent-household visits

For participants with known G6PD status, the study team will use the recruitment script to recruit participants in their homes. Only members of the household who have a known G6PD status from past epidemiological studies will be eligible for participation. Other household members will not be asked to participate in the study. He or she will be screened for inclusion in the study. The study team will explain the study and invite the person to participate. If the person expresses interest in participating in the study, she or he will be directed to a private space for consenting. Written consent or assent will be obtained from all participants. See detailed consent procedures and explanation of ethical considerations in sections 6.0 and 10.0.

5.2.4 Testing procedures at the point of care

All study procedures will be done in concordance with the health system; study procedures done at the clinics will be done in collaboration with clinic staff and the household surveys will be in collaboration by the health system agents and malaria control program.

Following completion of informed consent process, the study staff, who are trained in phlebotomy, will obtain a finger stick sample of no more than 30 μ l from the participant to perform the G6PD POC test, the POC hemoglobin test, and a thick blood film will be prepared to test for malaria as per the standard of care. Results of the POC tests will be recorded on data collection forms. If an invalid test result is obtained, a second finger stick sample will be obtained and a second test will be run. If an invalid test result is obtained a second time, the results will be recorded as invalid. The study staff will also draw a 4 mL tube of venous blood from the participant. The venous blood specimen will be taken using a standard venipuncture kit, and blood will be collected in the EDTA treated tube.

Slides will be viewed at the nearest health facility by a microscopist. Results will be delivered to patients by the health agents as per standard routine.

If the participants test positive for malaria or is found to be anemic based on hemoglobin thresholds from the WHO, the participant will be referred to a local health worker or the clinic for follow-up and case management (see Appendices C2 and C3).

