3.1 Statistical analyses

Data will be entered into a Microsoft Excel database with built-in validation rules to minimize data entry errors. Descriptive statistical analysis, including calculating point estimates, distribution, and frequencies of responses, will be used to summarize and characterize the study population.

3.1.1 Diagnostic accuracy and performance:

For the purposes of this study, an individual will be considered G6PD deficient (case) if they test positive by the spectrophotometric gold standard. The primary success criterion will be focused on the ability to identify G6PD deficient participants correctly, such that both the POC G6PD test and the spectrophotometric gold standard test should both accurately identify all G6PD deficient specimens (with < 20% normal) as deficient.

The performance of the POC G6PD against the spectrophotometric gold standard will be determined by calculating the sensitivity and specificity. Sensitivity and specificity of the SD Biosensor (SDB) G6PD assay were calculated as per Domingo et al. [14]. In summary, an adjusted male median will be calculated for both the POC G6PD and spectrophotometric gold standard test from where the 30%, 40%, 70% and 80% cutoff levels for the two tests will be used to categorically define G6PD deficient cases.

Sensitivity calculations will be determined by the following method: TTP=true and test positive (positive by reference assays according to case definition and positive by the POC G6PD test), FNTP=false negative true positive (positive by reference assays according to case definition and negative by the POC G6PD test). Sensitivity = $TTP/(TTP+FNTP)$.

Specificity will be determined by the following method: TPTN=test positive true negative (negative by reference assays according to case definition and positive by POC G6PD test), TTN=Test and true negative (negative by reference assays according to case definition and negative by POC G6PD test). Specificity= $TTN/(TTN+TPTN)$.

Sensitivity and specificity results will be reported using 95% confidence intervals.

3.1.2 Accuracy between G6PD activity and Hemoglobin methods:

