3.2 Sample size

The sample size for this study is based on the expected prevalence of G6PD deficiency at the study site and by data requirements set by WHO PQ [15]. This requires obtaining samples from participants with a range of G6PD activity levels. The WHO PQ process defines these levels as such:

Table 2. G6PD activity thresholds

Females	
Deficient	G6PD activity < 30% of the adjusted male median
Intermediate	G6PD activity 30%-80% of the adjusted male median
Normal	G6PD activity > 80% of the adjusted male median
Males	

Deficient	G6PD activity < 30% of the adjusted male median
Normal	G6PD activity > 30% of the adjusted male median

According to the Target Product Profile (TPP), the novel POC G6PD will need to be at least 95% sensitive for detecting G6PD activity levels at 30% to 80% of normal enzyme activity. Assuming a sensitivity of 95%, with a confidence interval of 95%, and a 1% to 2% maximum marginal error, a minimum of 162 participants with deficient and intermediate G6PD activity will be needed. To account for any possible device/diagnostic failures or compromised blood samples due to insufficient blood, signs of blood degradation, or contamination, to the sample size will need to increase by 20%. In addition, to ensure there are sufficient deficient and intermediate participants in the case of a lower-than-expected enrollment rate of these two groups occurs, at least 200 participants of each group should be included in the study. This additional enriched sample will also serve to meet the requirements of the WHO PQ. Eligible adults and children aged 2 years old and above will be recruited for potential participation though diagnostic performance analysis will not be segmented based on age.

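### A capillary POC test that is invalid twice has no place in the sensitivity and specificity formulas, so the all-deficient success criterion gives two different answers on the same data

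*Combined protocol and SAP*

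**What the plan says.** Section 5.2.4 sets the retest rule for the finger-stick test: "If an invalid test result is obtained, a second finger stick sample will be obtained and a second test will be run". It then closes the sequence: "If an invalid test result is obtained a second time, the results will be recorded as invalid". No analysis rule follows, there or elsewhere.

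Section 3.1.1 defines sensitivity as TTP/(TTP+FNTP) and specificity as TTN/(TTN+TPTN). The two sensitivity cells are "positive by reference assays according to case definition and positive by the POC G6PD test" and "positive by reference assays according to case definition and negative by the POC G6PD test". The specificity cells have the same form for reference-negative participants. The section says that performance will be determined from these two measures.

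The same section states the primary success criterion: the POC test and the reference assay "should both accurately identify all G6PD deficient specimens" as deficient, with a qualifier that limits this to specimens below 20% of normal.

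Section 3.2 mentions device failure only in setting the sample size. It adds 20% to allow for "any possible device/diagnostic failures or compromised blood samples due to insufficient blood" and for degraded or contaminated blood. Section 5.2.5 plans a further POC run on venous blood in the laboratory, and Table 1 lists venous and capillary as separate index-test sample types.

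**The concern.** A twice-invalid participant still gives venous blood and so can have a reference result. That person is a known case or non-case whom the capillary test did not classify. Because every accuracy cell needs a positive or negative POC result, the person appears in neither denominator. The estimates then describe only the samples that the device could read, although the primary objective covers reliability as well as accuracy, and no endpoint reports an invalid rate.

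The consequence is sharpest for the primary criterion, which is all-or-nothing. Deficiency is defined by the reference assay, so the criterion turns on the POC test, and a single unclassified deficient specimen can decide it. The results are meant to support WHO prequalification and product registration (section 2.0), so the scoring rule should be fixed before the data are seen.

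**Working it through.** **Inputs**
- Deficient participants expected: 2,000 × 5% = 100 (section 3.2). This reproduces the plan's figure. It counts activity below 30% of normal; the number below 20%, to which the criterion applies, is not given.
- Accuracy cells and criterion: section 3.1.1. Retest rule: section 5.2.4.
- Repeat-invalid rate: not in the documents. The counts and rates below are assumptions.

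**Step 1. What the formula does.** Let D be the deficient participants with a valid reference result, k those invalid twice, and f the false negatives among valid results.
- As written: (D − k − f)/(D − k).
- All D kept, repeat-invalid counted as not detected: (D − k − f)/D.

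The second equals the first multiplied by (1 − k/D), so leaving invalids out can never give a lower value than counting them as not detected. Specificity behaves in the same way among non-cases.

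**Step 2. Illustration with D = 100 and f = 0.** Intervals are exact (Clopper-Pearson) 95%. When all n valid results are correct, the lower limit is 0.025^(1/n).

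| Repeat-invalid, k | As written | Lower limit | All kept | 95% CI |
|---|---|---|---|---|
| 1 | 99/99 = 100% | 96.3% | 99/100 = 99% | 94.6% to 99.97% |
| 2 | 98/98 = 100% | 96.3% | 98/100 = 98% | 93.0% to 99.8% |
| 5 | 95/95 = 100% | 96.2% | 95/100 = 95% | 88.7% to 98.4% |

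The written formula returns 100% whatever the value of k.

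**Step 3. When some valid results are wrong.** Take the 95% sensitivity assumed in section 3.2 and the 96% specificity in Table 7 at the 30% threshold as the valid-only values. An assumed 2% repeat-invalid rate gives 95% × 0.98 = 93.1% and 96% × 0.98 = 94.1%.

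**Step 4. How easily one invalid could arise.** With independent results and repeat-invalid rate r, the chance of at least one among 100 is 1 − (1 − r)^100: 9.5% at r = 0.1%, 39% at 0.5%, 63% at 1% and 87% at 2%. For the smaller group below 20% of normal, the chance is lower.

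**Step 5. The criterion read two ways.** Suppose one specimen below 20% of normal is invalid twice and every other such specimen is correctly called.
- Literal reading: that specimen was not identified as deficient, so not all were. The criterion fails.
- Scored as sensitivity: the specimen is in no cell and sensitivity is 100%. The criterion is met.

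**The case against.** The strongest reply is that the plan never says invalids are excluded. That is right: exclusion follows from the cell definitions and is not a stated rule. A reader might infer that the sponsor chose to discard invalids, or that the criterion will be declared met wrongly. The documents support neither. Read literally, the criterion already fails on an unclassified specimen, and section 3.1.1 does not define it as sensitivity of 100%. What stands is that both readings are open.

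The venous replicate may also classify a participant whose capillary test failed twice, so it would be too strong to say that such a participant has no POC result at all. But no rule lets the venous result stand in for the capillary one. Table 1 keeps the two sample types apart, and comparing them is an endpoint of its own.

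A reader might take the 20% allowance in section 3.2 as a possible invalid rate. It is a sample-size inflation that also covers compromised blood, and an invalid here needs two failed finger-stick tests, so it cannot serve as one.

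Counting invalids as failures is a worst-case convention, and for specificity its use as the main analysis is debatable. Valid-only accuracy reported with the invalid rate is a legitimate alternative. This is a reason to report both.

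Finally, section 3.1.1 cites a published method for the accuracy calculation, and section 5.2.5 refers to WHO specifications for reporting. The latter sentence concerns performance characteristics and discrepant samples, and does not mention POC invalids. Whether either source covers them cannot be judged from the documents.

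**Conclusion.** The point holds as a gap with a known direction. The formulas as written condition on a readable POC result. Compared with counting repeat-invalids as not detected or not correctly classified, leaving them out can only keep or raise the reported accuracy. The primary criterion can pass or fail on identical data according to how it is scored, and one specimen is enough to change the answer.

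The effect on the estimates is probably modest: about one percentage point for each 1% of repeat-invalids. That size rests on assumed rates. The figures based on 100 participants are illustrative, because the criterion applies to a smaller group of unstated size. The plan should be corrected before analysis, but the design and data collection are not in question.

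**What to change.** In section 3.1.1:
1. For the capillary index test, judge the all-deficient criterion on every specimen below 20% of normal with a valid reference result, and count a repeat-invalid POC result as not identified.
2. Report sensitivity and specificity both ways: with repeat-invalids kept in the denominator (not detected for sensitivity, not correctly classified for specificity), and among valid results only.
3. Report first-attempt and repeat invalid rates by reference class.
4. State that the venous replicate is analysed as its own index-test sample type and does not replace an invalid capillary result.

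The cost is a few sentences and an extra column in the results table. No new testing is needed, but the data forms should keep the first-attempt invalids as well as the final result. The downside is that reported accuracy may be slightly lower.
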